### 6.6.2 Dose Modification in Part B (PUPs/MTPs)

Individual participant dose decisions are at the discretion of the investigator.

Recent studies have demonstrated that the timing of the first exposures to FVIII may be critical for the tolerance of the drug. The CANAL study showed that early intensive treatment, such as those required for surgery or severe bleeds, increased the risk for inhibitor development, whereas regular prophylaxis was associated with a lower risk. This observation was subsequently supported by studies demonstrating lower inhibitor rates in boys treated with low dose early prophylaxis in treatment centers in Germany.

Taking these observations into account, the following are treatment recommendations for PUPs/MTPs participating in Part B:

1. Prophylaxis can be started directly with 15 to 50 IU/kg (minimum dose: 250 IU) once per week; the starting dose may be tailored to the participant's weight or demonstrated bleeding tendency.
2. Alternatively, treatment can be initiated with an on-demand regimen. Prophylaxis should begin after a minimal number of on-demand FVIII exposures with KOVALTRY (no more than 2 to 3 bleeding events) or when the child is large enough to tolerate weekly infusion.
3. Avoid starting prophylaxis during a febrile illness or other identified inflammatory events.
4. Avoid surgery or need for high dose intensive treatment lasting more than 4 days during the first 20 ED.

5. KOVALTRY must not be given as prophylaxis for vaccinations.

After treatment with KOVALTRY begins, inhibitor testing every 3 to 5 ED is required until 20 ED are accumulated or in case of non-response to treatment.

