**Table 9–1: Analysis Populations**

Population	Description
Enrolled	All participants who signed the ICF or had an ICF signed on their behalf by a parent or legal representative.
Safety	Participants enrolled into the study and received at least 1 dose of study drug. The safety population will be used for the safety analysis.
Modified Intent-to-Treat (mITT)*	All study participants who have infusion/bleeding data from the EPD and/or CRF. The mITT population will be used for the efficacy analysis.
Per Protocol (PP)**	All mITT participants who completed study treatment and have at least 50 exposure days on study, without major protocol deviations.
PK analysis population	All participants with evaluable PK data will be included in the analysis of pharmacokinetic data.
ITI treatment analysis population	All participants who enter ITI treatment with study intervention will be included in the analysis for ITI treatment.

\* The ITT is inclusive of all enrolled and eligible patients. Modified ITT was introduced for this study as there is an additional condition that is to be met for participants included in ITT. This condition is that study participants need to have infusion/bleeding data from the EPD and /or CRF.

Therefore, ITT analysis population is renamed “modified ITT” for this study.

\*\* Only to be used if at least 5% of mITT participants (<12 or ≥12 years of age) are excluded from the PP population. The PP population is only in Part A; Part B will not have a PP population.

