#### **9.4.2 Primary Endpoint(s)**

All efficacy analyses will be performed on the mITT population. In case of PP population (Part A only), more than 5% of participants in one arm (children or adolescents/adults) are excluded from the mITT population, and analyses for primary and secondary endpoints will be repeated in the PP population. As the non-adherence to the EPD documentation is considered independent from the treatment efficacy, the exclusion of participants without bleeding/infusion data from the EPD does not interfere with the intention-to-treat principle. These participants are excluded in order not to dilute the treatment effect.

The primary endpoint in Part A is the ABR of all bleeding episodes during prophylaxis treatment, and it will be summarized by age group (<12 y, ≥12 y) separately.

The primary endpoint in Part B is the ABR of all bleeding episodes within 48 hours of a previous prophylaxis infusion.

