#### 4.2 Handling of Dropouts

Annualized number of total bleeds will be calculated for all subjects, including dropouts. Subjects who drop from the study will be included in a listing.

During the study, temporary discontinuation of study drug could happen, the duration of interruption of study intervention (i.e. prophylaxis treatment with KOVALTRY) should not be more than 2 weeks. Prolonged periods ( $> 2$  weeks) or repeated breaks in the prophylaxis schedule should be avoided and could result in the study participant treated as drop out, or being removed from the study.

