### **4.5 Data Rules**

All bleed and infusion data will be entered into the electronic patient diary (hospital infusions will be entered into an eCRF) and imported into SAS. If an infusion is given for a bleed and the bleed information is not provided, the infusion date will be used as the bleed date. Bleeds occurring before start of prophylaxis treatment with study medication will not be counted.

Bleeding rate will be annualized using the following formula:

Annualized bleeding rate [per year] =

365.25 [days per year] x (# of bleeding episodes in treatment period) / duration of treatment period [in days]

The treatment period (exclude optional ITI period) is defined as from the date and time of first study treatment, until the date and time of last infusion of study medication, or last visit, whichever is later.

- “24-hour rule”: No more than 1 bleeding episode in a calendar day is counted. If there is more than 1 bleeding episode in a calendar day, to determine which bleeding episodes are counted, priority is given to treated bleeding episodes, spontaneous or trauma bleeding episodes, then joint bleeding episodes. Otherwise, the first bleeding episode in the day is counted. Severity and treatment response will be the worst value of the bleeding episodes of the day. The bleeding site will be aggregated over all bleeding events from that day. Regardless of which bleed is selected, the time of the first bleed in the day will be used. All other infusions in the day for treating bleeds will be considered follow-up infusions.
- “72-hour rule”: A spontaneous joint or spontaneous muscle bleeding episode will not be counted if it occurs within 72 hours of a prior bleeding episode (or infusion for that bleeding episode) at the same site. For a bleeding episode to be affected by this rule, all sites listed for the bleeding episode must be the same sites specified in the previous bleeding episode. If the current and previous bleeds are both skin/mucosa bleeds, this rule does not apply. Infusions for such bleeding episodes will be considered to be follow-up infusions.

See example below how these bleeds will be counted.

- Subject 1 reported => in analysis data set

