#### Modified Intent-To-Treat (mITT)

All study participants who have infusion/bleeding data from the EPD and/or CRF will be included in mITT. The mITT population will be used for the efficacy analysis.

The ITT is inclusive of all enrolled and eligible patients. Modified ITT was introduced for this study as there is an additional condition that is to be met for participants included in ITT. This

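### In Part B, a child who leaves before any prophylaxis infusion stays in the efficacy set and receives a primary 48-hour ABR of 0 instead of being not evaluable

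*Protocol*

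**What the plan says.** Protocol Table 9–1 defines the mITT set, which carries all efficacy analyses, as "All study participants who have infusion/bleeding data from the EPD and/or CRF". SAP 5.1 uses the same condition. There is no second efficacy set for Part B: "The PP population is only in Part A; Part B will not have a PP population".

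Protocol 6.6.2 gives two ways to begin treatment in Part B. One is to start prophylaxis directly. The other is "Alternatively, treatment can be initiated with an on-demand regimen", with prophylaxis to follow after at most 2 to 3 bleeding events or once the child is large enough for weekly infusions. Protocol 7.2.2 likewise lets a PUP's first dose treat a bleed.

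On the endpoint, Protocol 9.4.2 says "The primary endpoint in Part B is the ABR of all bleeding episodes within 48 hours of a previous prophylaxis infusion". The one ABR formula (Protocol 9.4.1, SAP 4.5) multiplies the bleed count by 365.25 and divides by the days in the treatment period. That period starts at first study treatment, whatever the reason for the infusion.

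Two SAP rules bear on early leavers. SAP 4.2: "Annualized number of total bleeds will be calculated for all subjects, including dropouts". SAP 4.5: "Bleeds occurring before start of prophylaxis treatment with study medication will not be counted".

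**The concern.** These rules were written for children on prophylaxis. Applied to a child treated only on demand who then leaves, for example with a high-titer inhibitor or because the family withdraws, they return a number where there should be none. His 48-hour count is 0 by construction, his follow-up time is positive, and nothing in either document marks the result as missing or not evaluable. A child with several early bleeds would enter the primary summary with the best possible value.

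Part B plans about 6 children, and its results are to be set numerically against the earlier LEOPOLD trials. One artificial zero therefore shows in the mean, and it can only move the mean in the product's favour.

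**Working it through.** **Inputs from the documents.** Part B size about 6; planning mean 1.9 and SD 3.3 for the 48-hour ABR; stated probability of more than 80% that the mean of 6 is below 2.9; assumed inhibitor rate 35% to 54% (all Protocol 9.2.2 and SAP 3.1.2). ABR formula from Protocol 9.4.1 and SAP 4.5.

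**Step 1: reproduce the plan's figure.** Negative binomial by moments: k = 1.9² / (3.3² − 1.9) = 3.61 / 8.99 = 0.402. The sum over 6 children is negative binomial with size 6k, and a mean below 2.9 is a sum below 17.4. This gives P = 0.807, which agrees with the stated figure.

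**Step 2: the child's own values.** Assume 3 treated on-demand bleeds in 45 days and no prophylaxis infusion.
- Counting all bleeds: 365.25 × 3 / 45 = 24.4 per year.
- Primary endpoint: 365.25 × 0 / 45 = 0.

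The 0 does not depend on the assumed 45 days. Any positive follow-up gives it.

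**Step 3: effect on the unweighted mean.** One forced zero among 6: 1.9 × 5/6 = 1.58, a fall of 17%. P(mean below 2.9) becomes 0.868 with no change in bleeding. If the child is left out instead, the expected mean stays at 1.9 and P is 0.795 with 5 children.

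**Step 4: effect in the regression.** SAP 6.2.2 also plans, if applicable, a negative binomial regression with treatment duration as offset. Assume 45 days for this child, 270 days for the other five, k held at 0.402, and expected counts in place of observed ones. In years the times are 0.123 and 0.739. The fitted rate λ solves

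5 × (1.9 × 0.739 − 0.739λ) / (1 + 0.739λ/k) = 0.123λ / (1 + 0.123λ/k).

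At λ = 1.74 the left side is about 0.141 and the right side about 0.140. The rate falls from 1.9 to 1.74, or about 8%.

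**Step 5: is he also counted as bleed-free?**
- Protocol 9.4.1 counts bleeds from first study treatment. His on-demand bleeds count, so he is not bleed-free.
- SAP 4.5 does not count bleeds before the start of prophylaxis. On that wording he has no counted bleed. The rule does not say what applies if prophylaxis never starts.

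The two texts give opposite answers. The 0 in step 2 does not depend on which one is followed.

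**Step 6: how often?** The documents give no rate. As an illustration only, let a share s of inhibitor cases arise before prophylaxis and lead to exit. The chance of at least one such child in 6 is 1 − (1 − rate × s)⁶. For rates of 35% to 54% this is 19% to 28% at s = 10%, and 68% to 85% at s = 50%. The result depends almost entirely on s, which is assumed.

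**The case against.** **The case is narrow.** This stands. Families must agree to start prophylaxis (Protocol 5.1.2), and the on-demand phase is meant to be short. An inhibitor alone does not end participation: Protocol 6.8.3 requires withdrawal for a confirmed titer above 5 BU/mL that interferes with treatment. A reader might take the 35% to 54% as a guide to how many such children to expect, or work with two of 6 (mean 1.27, -33%). The documents do not support this, because that range is an overall inhibitor rate and not a rate before prophylaxis.

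**The fault is the clock, not the set.** This stands in part. If time at risk began at the first prophylaxis infusion, the child would have no denominator and his rate would be missing. It would therefore be wrong to say that the start of follow-up is irrelevant. The 0 needs both the open entry condition and a denominator that starts at first study treatment.

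**SAP 4.2 does not settle it.** This is correct. Its sentence on dropouts concerns total bleeds and does not name the 48-hour ABR. The 0 follows from the ABR formula and the mITT definition without it.

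**Nothing is decided on this number.** The study tests no hypothesis, and 2.9 is not a success criterion. The move from 0.807 to 0.868 is therefore only a way to show the size of the shift.

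**The child is not hidden.** Dropouts are listed, his bleeds enter the response-to-treatment summaries, and his inhibitor is reported. Data review (SAP 4.6 and 5.1) could also handle him. However, no criterion is set in advance for this case, and a choice made after seeing open-label data on about 6 children is best avoided.

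**Conclusion.** The point holds for the primary endpoint. As written, a Part B child with no prophylaxis infusion is in mITT and receives a 48-hour ABR of 0, when the endpoint is not defined for him. One such child among 6 lowers the expected unweighted mean by 17%, from 1.9 to 1.58. The regression estimate falls by about 8% under the assumed 45 and 270 days of follow-up. Both figures use the plan's mean of 1.9, and the regression figure also uses its SD of 3.3. The frequency is unknown and may be zero.

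A reader might go further and say that the plan definitely reports this child as bleed-free and gives him an ABR of 0 during prophylaxis. The documents do not support that as a firm statement. It rests on SAP 4.5 alone, which conflicts with the treatment period in Protocol 9.4.1 and is silent when prophylaxis never begins. What can be said is that he could appear bleed-free and that the two passages must be reconciled.

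**What to change.** In Protocol Table 9–1 and in SAP 5.1 and 6.2.1, state for Part B:
- The 48-hour ABR and the ABR during prophylaxis are evaluable only in mITT participants with at least one prophylaxis infusion, with time at risk starting at the first such infusion.
- A child who never receives prophylaxis but has bleeds is not counted among patients without bleeding episodes. Align SAP 4.5 with Protocol 9.4.1 accordingly.
- Such children are reported individually with their bleeds, follow-up time and inhibitor status, and remain in the treatment-of-bleeds and safety analyses.

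This takes a few sentences and changes no dose, schedule or clinical rule. The SAP is still based on protocol version 2.0 while the protocol is at version 4.0, so an update is a natural place for it.

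There are two costs. The primary estimate may rest on 5 children instead of 6. It also becomes conditional on having started prophylaxis, so a child with a poor early course leaves the primary summary. The individual reporting is there to keep that child visible.

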### 9.4 Statistical Analyses

The statistical analysis plan (SAP) will be developed and finalized before the first participant first visit (FPFV) and will describe the participant populations to be included in the analyses and procedures for accounting for missing, unused, and spurious data. This section is a summary of the planned statistical analyses of the primary endpoints in Part A and Part B of the study.

#### 9.4.1 General Considerations

There is no confirmatory comparison planned for this study; study results will be numerically evaluated and compared with the data in the completed LEOPOLD Clinical Trials.

Efficacy analyses outlined in this section only include the data from Part A or Part B (i.e., data from the Optional ITI Treatment are excluded).

For the efficacy endpoints, bleeding events will be presented as summary statistics by age groups.

The annualized bleeding rates for each participant are estimated via

$$\text{Annualized bleeding rate [per year]} = \frac{365.25 \text{ [days per year]} \times (\text{\# of bleeding episodes in treatment period})}{\text{duration of treatment period [in days]}}$$

The treatment period is defined as from the date and time of first study treatment until the date and time of last infusion of study medication, or last visit, whichever is later (not including the Optional ITI Treatment). Before this period is the screening period, after this period is the follow-up period.

Further, for the derivation of analysis variables for bleeding episodes, the following rules will apply:

- “24-hour rule”:  
No more than 1 bleeding episode in a calendar day is counted. If there is more than 1 bleeding episode in a calendar day, to determine which bleeding episodes are counted, priority is given to treated bleeding episodes, spontaneous or trauma bleeding episodes, then joint bleeding episodes. Otherwise, the first bleeding episode in the day is counted. Severity and treatment response will be the worst value of the bleeding episodes of the day. The bleeding site will be aggregated over all bleeding events from that day.
- “72-hour rule”:  
A spontaneous joint or spontaneous muscle bleeding episode will not be counted if it occurs within 72 hours of a prior bleeding episode (or infusion for that bleeding episode) at the same site. For a bleeding episode to be affected by this rule, all sites listed for the bleeding episode must be the same sites specified in the previous bleeding episode. If the current and previous bleeds are both skin/mucosa bleeds, this rule does not apply. Infusions for such bleeding episodes will be considered to be follow-up infusions.

Missing information on date and time of bleeding episodes will be substituted by the date and time of first treatment, if available.

Further handling of missing data will be described in the SAP.

#### **9.4.2 Primary Endpoint(s)**

All efficacy analyses will be performed on the mITT population. In case of PP population (Part A only), more than 5% of participants in one arm (children or adolescents/adults) are excluded from the mITT population, and analyses for primary and secondary endpoints will be repeated in the PP population. As the non-adherence to the EPD documentation is considered independent from the treatment efficacy, the exclusion of participants without bleeding/infusion data from the EPD does not interfere with the intention-to-treat principle. These participants are excluded in order not to dilute the treatment effect.

The primary endpoint in Part A is the ABR of all bleeding episodes during prophylaxis treatment, and it will be summarized by age group (<12 y, ≥12 y) separately.

The primary endpoint in Part B is the ABR of all bleeding episodes within 48 hours of a previous prophylaxis infusion.

#### 9.4.3 Secondary Endpoint(s)

Spontaneous bleeding episodes, trauma bleeding episodes, joint bleeding episodes, and other bleeding episodes types will be summarized separately.

Other efficacy variables are:

- ABR of treated bleeding episodes
- ABR of target joint bleeding episodes
- ABR of bleeding episodes within 48h of previous prophylaxis infusion (total, joint, spontaneous, trauma) [for Part A]
- ABR of all bleeding episodes during prophylaxis treatment [for Part B]
- Study participant's/caregiver's assessment of response to treatment of bleeding episodes (excellent, moderate, good, or poor)
- Physician's assessment of the response to treatment of bleeding episodes in minor surgery (excellent, moderate, good, or poor)
- Evaluate proportion of patients without bleeding episodes
- The number of infusions per bleeding episode
- Factor VIII usage (expressed as number of infusions and IU/kg per year, as well as IU/kg per event)
- Incremental recovery

All details of the analysis will be provided in the SAP.

#### 9.4.4 Safety Analyse(s)

Safety analysis will be performed separately for Part A, Part B, and Optional ITI Treatment.

Safety data will be summarized for all participants in the safety population for overall and by age groups respectively for Part A and summarized for Part B. Laboratory findings, AEs, concomitant medications, vital signs, and medical history data will be provided in participant listings. Laboratory values and vital signs will be summarized.

Individual listings of AEs (including age, AEs as reported, start, duration, severity, relation to study drug) will be provided. An AE is defined as treatment-emergent if it started or deteriorated after the first infusion and not later than three days after the last infusion in Part A or Part B. The incidence of treatment-emergent AEs will be summarized using the Medical Dictionary for Regulatory Affairs (MedDRA).

Inhibitor development as measured by Nijmegen-modified Bethesda assay will be summarized by time point and presented in participant listings. The purpose of the listing is to delineate the clinical factors that may be positively associated with development of the inhibitor. Confirmation of the first positive inhibitor titer (Bethesda  $\geq 0.6$  BU/mL) will require repeat measurement of a second different sample.

If the repeated inhibitor result is  $<0.6$  BU/mL without intervention, the inhibitor is not confirmed and should not be reported as an SAE. Inhibitors will be classified as being either low titer ( $\geq 0.6$  BU/mL and  $\leq 5$  BU/mL) or high titer based upon persistence of an inhibitor  $>5$  BU/mL. Proportions of participants with inhibitor will be presented in an overview table. Exact Clopper Pearson CI for the proportion will be given if any inhibitor exists.

The rate of inhibitor development will be summarized and described for both the pediatric and the adolescent/adult populations, and for the overall study population combined.

Safety analysis for optional ITI treatment is based on the ITI treatment set. Laboratory findings (inhibitor titer and recovery), AEs, concomitant medications, and EDs will be provided in participant listings. More details will be provided in the SAP.

#### **9.4.5 Pharmacokinetic Analyses**

Pharmacokinetic analyses will be described in the statistical analysis plan finalized before FPFV.

In addition, the pharmacokinetic data collected during this study might be analyzed by means of a population PK approach. The results of this evaluation may be reported in a separate Modeling and Simulation report. The actual sampling times will be used for PK evaluation.

#### **9.5 Interim Analyses**

In case the study will not be completed at the time of next KOVALTRY license renewal application in China, the most current results will be delivered for license renewal, and an interim analysis will be performed with all available data. This approach has been agreed with CDE.

#### **9.6 Data Monitoring Committee (DMC)**

Not applicable to this study.

## 10. Supporting Documentation and Operational Considerations

### 10.1 Appendix 1: Regulatory, Ethical, and Study Oversight Considerations

#### 10.1.1 Regulatory and Ethical Considerations

This study will be conducted in accordance with the protocol and with the following:

- Consensus ethical principles derived from international guidelines including the Declaration of Helsinki and Council for International Organizations of Medical Sciences (CIOMS) International Ethical Guidelines.
- Applicable ICH Good Clinical Practice (GCP) Guidelines.
- Regulations on Management of Human Genetic Resources of the People's Republic of China.
- The protocol, protocol amendments, ICF, Prescribing Information, Investigator Brochure, and other relevant documents (e.g., advertisements) must be submitted to an IRB/IEC by the investigator and reviewed and approved by the IRB/IEC before the study is initiated.
- Any amendments to the protocol will require IRB/IEC approval before implementation of changes made to the study design, except for changes necessary to eliminate an immediate hazard to study participants.

The investigator will be responsible for the following:

- Providing written summaries of the status of the study to the IRB/IEC annually or more frequently in accordance with the requirements, policies, and procedures established by the IRB/IEC
- Notifying the IRB/IEC of SAEs or other significant safety findings as required by IRB/IEC procedures
- Providing oversight of the conduct of the study at the site and adherence to requirements of 21 CFR, ICH guidelines, the IRB/IEC, European regulation 536/2014 for clinical studies (if applicable), and all other applicable local regulations

